8.1 STATISTICAL CONSIDERATIONS

General Considerations: Statistical analyses for this study will be the responsibility of the study statistician working through the Department of Biostatistics. Safety and efficacy analyses will be conducted on all evaluable patients. Parameter estimates and relevant summary statistics will be reported where appropriate. For continuous variables, summary statistics will include number of patients, mean, median, standard deviation, minimum and maximum. Categorical variables will be summarized using number of patients, frequency, and percentages. Additional exploratory analyses of the data will be conducted as deemed appropriate. Changes from this analysis plan will not require an amendment to the protocol unless it changes a significant feature in the protocol. The statistical analysis methods are detailed below. Standard statistical methods will be employed. Descriptive statistics, including means and standard deviations, or counts and percentages will be calculated. As a majority of the outcome variables are measured on the ordinal (Likert) scale, nonparametric statistical tests will be employed. The SAS® software, version 9.3,¹⁶⁶ will be used. A p-value of less than 0.05 will be considered statistically significant unless otherwise noted. Analysis plans specific to each hypothesis are further discussed below.

Analysis Sets: The definitions of the study populations are listed below:

Population	Definition
Intention-to-Treat	All patients who meet the eligibility criteria and are registered for the study irrespective of their compliance to the planned course of treatment.
Per Protocol Set	All patients who complied with the protocol sufficiently to ensure that these data would be likely to exhibit the effects of treatment, according to the underlying scientific model. Compliance covers such considerations as exposure to treatment, availability of measurements and absence of major protocol violations.

Population	Definition
Safety	All patients receiving at least one dose of study drug are included in the analysis of safety, unless otherwise noted.

Participant Characteristics: Participant demographics and baseline characteristics will be listed and summarized for the Intent-to-Treat population, including age, gender, ethnicity, height, weight and medical history.

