Demographic and baseline measurements will be compared between the two groups. Variables measured on an interval scale (e.g., age) will be compared between the two groups with a Student's t-test. Variables that are not normally distributed will be tested with the Wilcoxon rank sum test. The chi-square test or Fisher's exact test will be employed for variables measured on the nominal scale (e.g., gender).

Concomitant Medications: Concomitant medications will be summarized.

Participant Disposition: Disposition will be tabulated showing the number of those entered and discontinued for any reason. Reasons for discontinuation will be listed and summarized.

Compliance: Number of subjects who are compliant with respect to pill taking (defined as $\geq 75\%$ of prescribed study medication consumption) will be reported.

Subject Replacements: Subjects who discontinue the study will not be replaced.

Sample Size: The sample size is based on the sample size needed for the primary and secondary efficacy analyses. For the primary outcome (proportion of participants who have a decrease of at least 3 points in their Irritability Domain Score), thirty-three participants per group are necessary to detect a difference of 40% having a successful decrease in irritability in one group versus 80% in the other, using a chi-square test with a power of 90% and an alpha of 0.05. This is the effect size we observed in our prior amantadine single-site study.⁴³ For the secondary outcomes, the sample size for the Wilcoxon rank sum test was calculated using the formulas derived by Noether.¹⁶⁷ Thirty-three people are needed in each group to ensure a power of 80%, with an alpha of 0.05, and $p = \text{probability}(Y > X) = 0.70$, where Y and X are random samples from the two populations (groups). Under the null hypothesis $p = 0.50$. To allow for a 10% loss-to-follow up, 37 participants will be enrolled into each of the 2 study arms for a total sample of 74.

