Hypothesis 1b: Among individuals with TBI of >6 months duration, BUSP will result in statistically significant improvement in scores of one or more of the following measures compared to placebo: a) observer and participant ratings of NPI and NPI-Distress Irritability domain scores, b) observer and participant ratings of NPI and NPI-Distress Aggression domain scores, c) participant ratings of TBI-QOL Anger bank, d) observer ratings of SASNOS, e) observer and participant ratings of Global Impression of Change, f) physician ratings of Clinical Global Impressions.

The primary analysis will be intention-to-treat. For Hypothesis 1a, the primary outcome, the percent of participants who are considered to have meaningful reduction in irritability (decrease of at least 3 points in the NPI Irritability Domain Score) from baseline to 91 days, will be compared between the two groups (those receiving active drug and

placebo) using a chi-square test. A logistic regression model will be used to adjust for depression and possible demographic and baseline differences between the two groups and a post-hoc secondary analysis will examine the factors (including depression and anxiety) influencing the effect of BUSP on the primary outcome by including group interaction in the logistic model. For Hypothesis 1b, the change in the observer-rated NPI Irritability Domain Score from baseline to 91 days will be compared between the two groups using a Wilcoxon rank sum (Mann-Whitney) test for ordered categories. The secondary outcomes will also be compared between the two groups using Wilcoxon rank sum tests. For the secondary outcomes, Hochberg's step-up Bonferroni method will be used to control for multiple testing. Secondary analyses will include repeating the analyses above using the PPS population. Wilcoxon rank sum tests will also be performed for separate subgroups such as females, males, participants with injury caused by motor vehicle crashes or falls to test whether BUSP can be efficacious for these separate subgroups. In addition, if a substantial number of participants have depression, a preliminary analysis of the effect of BUSP on PHQ-9 may be performed. The effect of BUSP on GAD-7 will also be performed.

Safety Analysis: Hypothesis 2: BUSP will be tolerated as measured by number and types of the adverse events in the treatment group compared to the placebo group.

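### Subgroup efficacy is to be judged by separate within-subgroup Wilcoxon tests on an open list, with no stated adjustment and no treatment-by-subgroup contrast tied to them, which invites false subgroup claims

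*Combined protocol and SAP*

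**What the plan says.** Section 8.1, Efficacy Analyses, after the primary and secondary comparisons: "Wilcoxon rank sum tests will also be performed for separate subgroups such as females, males"; the sentence goes on to list people injured in motor vehicle crashes or falls. The stated purpose is "to test whether BUSP can be efficacious for these separate subgroups". No outcome is named for these tests, no subgroup sizes are given, and there is no rule for reading the results.

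Three other statements in section 8.1 bear on this:

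- The significance level comes from General Considerations: "A p-value of less than 0.05 will be considered statistically significant unless otherwise noted". Nothing different is noted for subgroups.
- Multiplicity control is stated once: "For the secondary outcomes, Hochberg's step-up Bonferroni method will be used to control for multiple testing". The text does not say whether subgroup tests are covered.
- An interaction analysis exists, by adding a group interaction to the logistic model: a "post-hoc secondary analysis will examine the factors (including depression and anxiety) influencing the effect of BUSP on the primary outcome". It concerns the binary responder outcome only, and it does not say whether sex or cause of injury enter.

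Randomisation (section 4.1) is stratified on depression only, so neither sex nor cause of injury is balanced by design.

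**The concern.** A test of drug against placebo inside females, and another inside males, gives two separate verdicts and no comparison between them. When each subgroup holds only part of a sample that was sized for the whole, one verdict will often be significant and the other not, even if the drug works equally well in both. When the drug does nothing, each further test is another chance of a false positive, and an illustrative list sets no limit on how many there are.

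The rationale in section 2.0 is that physicians and patients need evidence for choosing among agents person by person. A published statement that buspirone works in one sex or after one type of injury is the kind of result that would be used for that choice, so a spurious one has a practical cost even though the analysis is secondary.

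**Working it through.** **Inputs from the plan (section 8.1, Sample Size).** "Thirty-three people are needed in each group to ensure a power of 80%, with an alpha of 0.05", with P(Y>X) = 0.70 against a null of 0.50, using Noether's formula. Allowing for 10% loss gives 37 per arm, 74 in total. Sidedness is not stated; two-sided reproduces the figure.

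**Assumptions, not in the documents.** The subgroup shares; 1:1 allocation within each subgroup; for the simulations, continuous normal data with a shift giving P(Y>X) = 0.70.

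**1. Reproduce the plan's figure.** With c = 0.5,

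N = (1.960 + 0.842)² / [12 × 0.25 × (0.70 − 0.50)²] = 65.4, so 33 per arm. This matches.

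Power at N = 66 is Φ(√(3 × 66) × 0.20 − 1.96) = Φ(0.854) = 80.4%.

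**2. Power in each part of a split.** The formula is the same, with the subgroup's N. At 50:50, N = 33 and power is Φ(√99 × 0.20 − 1.96) = Φ(0.030) = 51.2%.

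**3. Chance that exactly one of two complementary subgroups is significant when the true effect is the same.** The two parts share no participants, so with powers a and b this is a(1 − b) + b(1 − a).

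| Assumed split of 66 | Power, larger / smaller | Exactly one significant | Both significant |
|---|---|---|---|
| 50:50 | 51% / 51% | 50% | 26% |
| 67:33 | 63% / 37% | 53% | 23% |
| 70:30 | 65% / 34% | 55% | 22% |
| 75:25 | 68% / 29% | 58% | 20% |

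At 70:30, for example, 0.653 × 0.662 + 0.338 × 0.347 = 0.55. With all 74 evaluable, 50:50, 67:33 and 75:25 give 49%, 53% and 58%. Simulated Mann-Whitney tests at roughly those three splits of 66 gave 50%, 54% and 61%.

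**4. Sensitivity to the effect size (50:50, N = 66).** Exactly one is significant in 28% of trials at P(Y>X) = 0.60, 44% at 0.65, 50% at 0.70, 42% at 0.75 and 26% at 0.80. The quantity 2a(1 − a) peaks at a = 50%, and the planning value gives a = 51%, so it sits almost at the maximum.

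**5. No true effect.** Four independent tests would give 1 − 0.95⁴ = 18.5%. Sex and cause subgroups overlap in the same participants, and simulation with 66 participants gives about 15% to 16% for at least one p < 0.05 on one outcome. If crashes and falls are one combined subgroup there are three tests, and the simulated figure is about 11% to 12%.

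**The case against.** The strongest reply is that the plan never says the subgroups will be compared, nor that a non-significant result means the drug fails in that subgroup. That is correct. A reader might infer that the plan itself sets out to claim differing effects; the text does not support this. What it sets out is an efficacy verdict within each subgroup. The comparison is a step that readers of the results would add, and nothing in the plan guards against it.

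Three further points stand in part:

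- A reader might infer that sex and cause of injury are excluded from the interaction analysis. They are not: depression and anxiety are given as examples and the list is open. What can be said is that the interaction is not linked to these subgroup tests and does not cover the ordinal NPI-Irritability change.
- A reader might infer that the subgroup tests are placed outside the Hochberg procedure. The plan is silent on this. The 0.05 level follows from the general default because no adjustment is stated.
- The planning effect is close to the worst case for discordance, and the wording on crashes and falls can be read as one subgroup. Both ranges are therefore shown.

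It can also be said that interaction tests have little power here. That is true, but within-subgroup tests are underpowered too, and they answer a different question.

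**Conclusion.** The concern holds as a weakness in how subgroup results would be produced and read. If buspirone had the planning effect equally in both sexes, the plan would show significance in exactly one sex in roughly half of trials or a little more (50% to 58% across the assumed splits), and in both sexes in only about 20% to 26%. For effects away from the planning value the discordance is lower, 26% to 44% at an equal split over the values checked, but not negligible. Under no effect, the chance of at least one nominally significant subgroup is about 11% to 16% on one outcome, depending on whether there are three or four tests. It would rise with more subgroups or outcomes, and the plan limits neither.

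These figures rest on assumed subgroup shares and balanced arms within subgroups. The shares change the size, not the direction.

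A reader might go further and infer that the trial's main conclusions are compromised. They are not: the primary chi-square test and the Hochberg-controlled secondary comparisons do not depend on the subgroup tests.

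**What to change.** In section 8.1, Efficacy Analyses:

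- Replace the illustrative list with a closed one (sex and cause of injury, with categories defined) and name the outcome or outcomes to be analysed.
- For the responder outcome, add treatment-by-sex and treatment-by-cause terms to the logistic model already planned.
- For NPI-Irritability change, compare the subgroup effects by an interaction: either an ordinal model, or the difference between subgroup estimates of P(Y>X) to stay nonparametric.
- Report each subgroup's effect with a 95% confidence interval, base no efficacy claim on a within-subgroup p-value, and label the results exploratory.

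The cost is SAP wording; no new data are needed. An ordinal model adds an assumption that the plan's rank tests avoid. Interaction contrasts will be imprecise. On Noether's null variance, each half of 66 has standard error 1/√99 = 0.10 for P(Y>X), so the difference has √2 × 0.1005 = 0.142. A true contrast of 0.70 against 0.50 would then be detected with power of about Φ(0.20/0.142 − 1.96) = 29%. The intervals would show that imprecision openly, and a non-significant interaction should not be read as proof of a uniform effect.
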